### **13.7 External Review of the Study Conduct at Participating Sites**

All study-related materials at the site are subject to external review to ensure the safety of the subjects, the integrity of the study data, and compliance with all applicable regulatory and oversight requirements.

There are several different classes of review:

- Monitoring — review by the Sponsor or authorized representatives, typically from the CRO coordinating the clinical conduct of the trial;
- Audits — independent review by the quality assurance department of the Sponsor or authorized representatives, potentially from an organization not involved in the clinical conduct of the study;
- Regulatory review — performed by representatives of regulatory authorities with responsibility for oversight of the trial or approval of the investigational agent. These authorities may be from the country where the site is located or from another country.

Activities during these on-site reviews may include, but are not limited to:

- Inspection of the facilities (e.g., clinical and administrative areas, pharmacy, laboratory);
- Review of the site trial master file, including documentation related to the protocol, the Investigator, and other study site personnel; correspondence to and from the IRB, the Sponsor, and their representatives;
- Review of standard operating procedures and current practices relating to clinical and pharmacy activities, data handling, the IEC oversight and the informed consent process;
- Review of source documents supporting all data collected during the study (e.g., inclusion/exclusion criteria, informed consent forms, HIPAA authorizations, adverse events records, expedited event reporting, efficacy endpoints);
- Resolution of any discrepancies noted.

Monitoring and auditing visits on behalf of the Sponsor will be scheduled with the Investigator in advance and will be conducted at a reasonable time. To facilitate these visits, the Investigator will assure that the following are available:

- appropriate space, facilities and access to all source documents (including access to computerized records either electronically or as complete print outs);
- consent forms, CRFs, SAE forms, and medical records for all screened and enrolled subjects;
- timely access to site personnel, including the Investigator, sub-Investigator(s), and other study personnel on the day of the visit to resolve any questions that arise.

Regulatory authorities may visit and review the site and/or Investigator during or after the study and may or may not notify the Investigator or the Sponsor in advance. The Investigator will fully cooperate with regulatory audits conducted at a reasonable time in a reasonable manner. The Investigator will notify the Sponsor immediately of any contact by or communication from regulatory authorities regarding the study.

### 13.8 Resolution of Deficiencies

The Investigator agrees to take promptly any reasonable steps requested by the Sponsor to resolve any deficiencies identified as a result of monitoring, audits, inspections, protocol deviations or review of any other study documentation. Failure to take adequate remedial action can result in suspension or termination of the study at the site.

### 13.9 Study Closeout

The study will be considered complete when all of the following have occurred:

- All treated subjects have completed all scheduled visits plus any unscheduled follow-up required by AEs;
- All CRFs have been completed, submitted and all queries resolved;
- The trial database has been locked.

The Sponsor or designee will then conduct a study closeout visit, which may include, but is not be limited to, any of the following:

- Review the site Trial Master File to assure all required regulatory documents are current and complete;
- Resolve any open issues from prior monitoring, audit or inspection visits;
- Review the site's provisions for meeting the requirements for retention study records;
- Discuss possible future site audits;
- Review the Sponsor's publication policy;
- Confirm compliance with requirements for notifying the IRB of study events, including closure;
- Collect any unused study materials for either return to the Sponsor or disposal in a manner approved by the Sponsor.

### 13.10 Record Retention

All study-related materials at the site (e.g., source documents, CRFs, Trial Master File) will be retained according to ICH guidelines and applicable regulations.

The study drug is being developed under a U.S. Investigational New Drug (IND) application; regulations require all study-related materials be retained for **at least 2 years after** one of the following events:

- approval of a New Drug Application based on this study;
- notification by the Sponsor that no further application will be filed.

The Investigator will use the following procedures regarding retained records:

- Contact the Sponsor **before** destroying any records pertaining to the study;
- Provide the Sponsor an opportunity to collect the records;
- Obtain written permission from the Sponsor to destroy the records;
- Notify the Sponsor if the Investigator plans to leave the institution so that arrangements can be made for the transfer of records;

Clinical and laboratory samples that are unstable may be disposed with the written approval of the Sponsor.

### **13.11 Data Management**

A detailed Data Management Plan will be prepared separately and approved by the Sponsor.

## 14. STATISTICAL METHODS

The sections below indicate the overall structure and approach to the analysis of this study. A detailed Statistical Analysis Plan (SAP) incorporating these sections below will be prepared separately and approved by the Sponsor. The SAP will define populations for analysis, outline all data handling conventions, including software, and specify additional statistical methods to be used for analysis of safety, efficacy and pharmacokinetics.

### 14.1 Power and Sample Size

Our data from Tanzania indicate that rates of TB infection defined by a positive tuberculin skin test increase from 0% at birth to approximately 70% in adulthood (14). Data from South Africa using an IGRA to define TB infection indicate that approximately 30% of 12-14 year olds already have TB infection, and that 7-14% develop new TB infection each year (15-17). Since adult rates of TB infection as measured by tuberculin skin test surveys are similar in Tanzania and South Africa, we estimate conservatively that Tanzanian adolescents have an annual rate of new TB infection of 7% per year as defined by conversion of an IGRA from negative to positive. We hypothesize that a DAR-901 booster regimen will be 50% effective in preventing new TB infection among adolescents in Tanzania.

We anticipate identifying 650 IGRA-negative 13-15 year olds by screening 1000 subjects in this age range. Assuming a 7% annual rate of infection, and 5% loss to follow-up per year, 650 subjects randomized to vaccine or placebo and followed for an average of 1.75 years will provide 80% power to detect vaccine efficacy of 50%.

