### ***2.8.5 Determination of Sample Size***

The sample size of 650 subjects (325 in each treatment group) is based on an expected 7% annual IGRA conversion rate among placebo recipients who remain IGRA-negative at 2 months (pre-dose 2; IGRA conversions before dose 2 may represent TB infection acquired prior to the dose 1). The sample size is calculated with 80% power to detect vaccine efficacy of 50% in preventing TB infection. Loss to follow-up is estimated at 5-10% per year. A blinded interim analysis will be conducted after results of the 14 month IGRA are available on 200 subjects. The study duration and number of repeat IGRAs will be increased if needed to detect sufficient endpoints.

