### 14.3 Statistical Methods

The statistical analysis is divided into two parts.

1) *Risk factors for TB infection.* All screened subjects will be included in this analysis which will compare subjects who test positive for IGRA at baseline and those who test negative. Demographics, behavioral and epidemiologic risk factors, and other questionnaire items will be compared. Pearson chi-square, Fisher's exact, t-test and Wilcoxon-Mann-Whitney tests will be used as appropriate.

2) *Effect of DAR-901 vaccine on preventing new TB infection.* New TB infection is defined as conversion from a negative IGRA at 2 months after enrollment (first dose of vaccine) to a positive IGRA at any time thereafter. Subjects who convert from IGRA negative at screening to positive indeterminate or invalid at 2 months (administration of study dose #2) will be assumed to represent TB infection acquired before administration of study dose #1 and will be excluded from the endpoint analysis. All other subjects who complete the visit for dose #2 and remain IGRA negative will be included. The primary endpoint is time to new TB infection (= new IGRA-positivity), subject to right censoring. The primary test statistic will be a log-rank test comparing the two study arms (intention-to-treat), with  $p < 0.05$  defined as significant. The proportion converting over time will be calculated using Kaplan-Meier statistic. To account for the interval censoring in the capture of IGRA conversion, we will apply methods for discrete time-to-events. The secondary endpoint is time to persistent new TB infection (= new IGRA-positivity which remains positive on a second IGRA at  $\geq 3$  months later) and analysis will be conducted using the same methods described above.

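### The 80% power stated for 50% vaccine efficacy does not follow from section 14.1's inputs under the usual two-sided log-rank reading, which gives about 69–74%

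*Protocol*

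**What the plan says.** Protocol section 14.1 sets out the calculation. The effect is given as "We hypothesize that a DAR-901 booster regimen will be 50% effective in preventing new TB infection among adolescents in Tanzania". The other inputs are "Assuming a 7% annual rate of infection, and 5% loss to follow-up per year", and 650 randomised subjects "followed for an average of 1.75 years will provide 80% power to detect vaccine efficacy of 50" per cent.

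Synopsis section 2.8.5 gives the allocation, "The sample size of 650 subjects (325 in each treatment group", and repeats the claim: "The sample size is calculated with 80% power to detect vaccine efficacy of 50% in preventing TB infection". Its loss assumption differs: "Loss to follow-up is estimated at 5-10% per year". It also provides that "The study duration and number of repeat IGRAs will be increased if needed to detect sufficient endpoints".

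Section 14.3 names the analysis, "The primary test statistic will be a log-rank test comparing the two study arms (intention-to-treat", and sets significance at p < 0.05. The protocol does not say whether the test is one- or two-sided, whether 50% efficacy is a hazard reduction or a reduction in cumulative risk, which formula was used, how many conversions are required, or whether 1.75 years is already net of loss.

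**The concern.** The protocol gives enough inputs to recompute the power of its primary test, and the ordinary reading does not return the stated figure. A log-rank test at p < 0.05 with no mention of direction is normally taken as two-sided, and efficacy for a time-to-event endpoint is normally one minus the hazard ratio. On that reading the trial expects 10 or more conversions fewer than 80% power requires.

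Two things are at stake. Readers who take 80% at face value will give a null result more weight than the design earns. And the extension clause in 2.8.5 refers to a sufficient number of endpoints without giving one, so a wrong power figure leaves that decision without a sound reference.

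**Working it through.** **Inputs.** 325 per arm (2.8.5); 7% annual conversion on placebo, 5% annual loss, average 1.75 years, efficacy 50% (14.1); log-rank test, p < 0.05 (14.3). *Assumed:* two-sided test; exponential conversion and loss; loss hazard μ = −ln(0.95) = 0.0513 per year. The 7% can be an annual risk, λ = −ln(0.93) = 0.0726, or a rate, λ = 0.07. Both are shown.

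**Expected conversions at hazard ratio 0.5.** For each arm, 325 × λ/(λ+μ) × [1 − exp(−(λ+μ) × 1.75)]; the vaccine arm uses λ/2.
- λ = 0.0726: 37.1 + 19.1 = 56.2
- λ = 0.07: 35.9 + 18.5 = 54.3

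**Conversions needed for 80% power, two-sided 5%.**
- Schoenfeld: 4 × (1.960 + 0.842)² / (ln 2)² = 65.3, so 66
- Freedman: (1.960 + 0.842)² × (1.5/0.5)² = 70.6, so 71

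**Power with D conversions.** Schoenfeld: Φ(½ √D ln 2 − z). Freedman: Φ(√D/3 − z). z = 1.960 two-sided, 1.645 one-sided.

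| Hazard ratio 0.5, 1.75 years | D | Schoenfeld, two-sided | Freedman, two-sided |
|---|---|---|---|
| No loss | 56.8–58.8 | 74–76% | 71–72% |
| 5% per year (14.1) | 54.3–56.2 | 72–74% | 69–71% |
| 10% per year (upper end in 2.8.5) | 51.9–53.7 | 70–72% | 67–69% |

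Simulated two-sided log-rank tests at 5% loss gave 70–71%.

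**Trying to reproduce 80%.**
- *One-sided 5%, hazard ratio 0.5, 5% loss:* Schoenfeld 82–83%, Freedman 79–80%.
- *Two-sided, efficacy as a cumulative risk ratio:* 7% × 1.75 = 12.25% against 6.125%, so the implied hazard ratio is ln(0.93875)/ln(0.8775) = 0.484. With no loss, D = 325 × 0.18375 = 59.7, and power is 80.1% (Schoenfeld) or 76.7% (Freedman). With 5% loss, D = 57.2, and power is 78.4% or 74.9%.
- *The same with compounded risk:* 1 − 0.93^1.75 = 11.93% against 5.96%. With 5% loss, power is 77.2% (Schoenfeld) or 73.7% (Freedman).
- *Simulation of the two risk-ratio cases at 5% loss:* 75–76%.

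So 80% can be approached by two routes: a one-sided test, or a two-sided Schoenfeld calculation on a cumulative risk ratio that ignores loss.

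**Efficacy detectable with 80% power (two-sided, 5% loss).** With λ = 0.0726, a hazard ratio of 0.470 gives D = 55.1, and ½ × √55.1 × 0.755 = 2.80 = 1.960 + 0.842. That is an efficacy of 53%. The same equation gives 54% with λ = 0.07, and the Freedman form gives 55–56%.

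**Subjects for 80% at hazard ratio 0.5.** 650 × 66/56.2 ≈ 763 up to 650 × 71/54.3 ≈ 850 in total.

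**The case against.** The sponsor can fairly say that the protocol commits to neither a two-sided test nor a hazard-ratio scale, and that either may be settled in the statistical analysis plan. A two-sided origin for 80% also exists: the Schoenfeld figure on 12.25% against 6.125%. This stands. A reader might infer that 80% can come only from an undeclared one-sided test, and the documents do not support that. The risk-ratio route does not rescue the claim, however, because it reaches 80% only without the 5% loss that 14.1 assumes, and only by Schoenfeld.

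The 1.75 years may already be net of loss. If the final visit is at 24 months, 22 months after Visit 2 with 5% annual loss averages (1 − 0.95^(22/12))/0.0513 = 1.75 years. Deducting loss again would then double-count it. Power at hazard ratio 0.5 is in that case about 71–76% by formula and 72–73% by simulation, which is still short.

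Follow-up may also run longer. Section 2.8.5 allows extension, and Table 1 adds an IGRA up to 12 months after Visit 5 with reconsent. If follow-up reached about 2.8 years after Visit 2, two-sided power would be about 83–90% at 5–10% annual loss. A reader might therefore go too far in concluding that the finished trial must be underpowered. But 14.1 claims 80% at 1.75 years, not after an extension.

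Finally, 5% lies within 5–10%, so the two loss statements do not strictly conflict. They do leave one power figure resting on two assumptions.

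**Conclusion.** The stated 80% is not delivered by section 14.1's own inputs under the conventional reading. With a two-sided 5% log-rank test, hazard ratio 0.5, 5% annual loss and 1.75 years, power is about 69–74%, from 54–56 conversions against 66 (Schoenfeld) or 71 (Freedman) needed. A true 50% effect would be missed about 26–31% of the time rather than 20%. On the cumulative-risk scale the shortfall is smaller, with power about 74–78% at 5% loss. Moving to 10% loss costs about a further 2 points.

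This rests on a two-sided test, which the protocol does not state, and on constant conversion and loss rates. A one-sided 5% test would roughly support the claim, but that choice would then have to be written beside it. The point concerns a figure and its missing definitions; it does not show that the design has to change.

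**What to change.** In sections 14.1 and 2.8.5:

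- Restate the power as about 70–74% (two-sided 5%, hazard ratio 0.5, 5% annual loss, average 1.75 years), or as 80% power for an efficacy of roughly 53% or slightly higher.
- Use one annual loss rate in both sections.
- State the sidedness of the test, the scale of efficacy, the formula, and whether 1.75 years is net of loss.
- Give the number of conversions needed for 80% power at 50% efficacy (66 by Schoenfeld), as the reference for what counts as sufficient in the extension clause of 2.8.5. Whether to make it a binding trigger is the sponsor's choice.

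Section 2.4.2 states no power figure and needs no change. The cost is wording in two sections and a less favourable stated power; no extra subjects are needed.

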### 14.2 Analysis Populations

- *Safety population* – all subjects who received at least one dose of the study medication.
- *Efficacy population (ITT)* – all subjects, as randomized, with a negative IGRA at enrollment and at the time of the 2 month (=dose 2) study visit. This is the Intent-to-Treat (ITT) population.

### 14.3 Statistical Methods

The statistical analysis is divided into two parts.

1) *Risk factors for TB infection.* All screened subjects will be included in this analysis which will compare subjects who test positive for IGRA at baseline and those who test negative. Demographics, behavioral and epidemiologic risk factors, and other questionnaire items will be compared. Pearson chi-square, Fisher's exact, t-test and Wilcoxon-Mann-Whitney tests will be used as appropriate.

2) *Effect of DAR-901 vaccine on preventing new TB infection.* New TB infection is defined as conversion from a negative IGRA at 2 months after enrollment (first dose of vaccine) to a positive IGRA at any time thereafter. Subjects who convert from IGRA negative at screening to positive indeterminate or invalid at 2 months (administration of study dose #2) will be assumed to represent TB infection acquired before administration of study dose #1 and will be excluded from the endpoint analysis. All other subjects who complete the visit for dose #2 and remain IGRA negative will be included. The primary endpoint is time to new TB infection (= new IGRA-positivity), subject to right censoring. The primary test statistic will be a log-rank test comparing the two study arms (intention-to-treat), with  $p < 0.05$  defined as significant. The proportion converting over time will be calculated using Kaplan-Meier statistic. To account for the interval censoring in the capture of IGRA conversion, we will apply methods for discrete time-to-events. The secondary endpoint is time to persistent new TB infection (= new IGRA-positivity which remains positive on a second IGRA at  $\geq 3$  months later) and analysis will be conducted using the same methods described above.

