#### 2.2.2 Secondary Objectives

To identify risk factors for infection with TB among adolescents in Tanzania.

To identify subject characteristics associated with vaccine induced protection against infection with TB.

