## 2.4 Study Design

This is a Phase II 3-injection randomized, controlled trial of DAR-901 to be conducted in 13-15 year old adolescents in Tanzania previously immunized with BCG. The goals are to establish the safety and efficacy of DAR-901 in preventing infection with TB. The 1 mg level corresponds to the dose of SRL 172 used in the successful DarDar Trial.

Doses will be administered by intradermal (ID) injection in the deltoid area at 0, 2 and 4 months. In the Phase 2 study of SRL 172 conducted in Finland, significant immunogenicity was induced by 3 injections [1]. The dose intervals and route of administration are consistent with all previous studies of SRL 172.

All subjects will be screened by the T-spot® IGRA (Oxford Immunotec, Oxford, England) for evidence of TB infection. All screened subjects will have height and weight measured and will have a structured interview to identify risk factors for TB infection (=positive IGRA). IGRA-positive subjects will be referred for further evaluation and will not be entered in the immunization phase of the trial.

It is estimated that 1000 adolescents will need to be screened to enroll a total of 650 IGRA-negative adolescents in the immunization phase of the trial. Subjects will be and randomized 1:1 to DAR-901 or saline control at 0, 2 and 4 months. IGRA testing will be repeated before dose 2, at 14 months, and again at end of study or 24 months, whichever comes first.

The risk factor study will employ a cross-sectional analysis comparing IGRA-positive and IGRA-negative adolescents at baseline (estimated 650 IGRA-negative and 350 IGRA-positive subjects). Risk factor analysis will also be conducted on subjects enrolled in the immunization phase who develop new TB infection during the study.

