### **2.8.4 *Risk factor Analyses***

Data will be analyzed using descriptive and analytic statistics. Variables will include household or community contact with TB, residence or exposure to congregate settings such as hospitals, correctional facilities, nursing homes, and orphanages; room size; ventilation systems (windows); airflow patterns; use of public transportation (e.g. daladala buses); socioeconomic status, nutritional status, and underlying disease (e.g., diabetes).

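### Section 14.3(1) names only unadjusted two-group tests for the risk-factor objective, although the listed exposures plausibly overlap; a pre-specified logistic model should be added

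*Protocol*

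**What the plan says.** Protocol Section 2.2.2 lists as a secondary objective "To identify risk factors for infection with TB among adolescents in Tanzania", and Section 6.2 repeats it. Section 16.5 foresees a separate publication on it.

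Section 2.4 describes a cross-sectional baseline comparison with "estimated 650 IGRA-negative and 350 IGRA-positive subjects".

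Section 14.3(1) covers the analysis of all screened subjects. It says that "Demographics, behavioral and epidemiologic risk factors, and other questionnaire items will be compared", and then that "Pearson chi-square, Fisher's exact, t-test and Wilcoxon-Mann-Whitney tests will be used as appropriate". No regression, stratification or adjusted estimate for risk factors appears there or elsewhere in the protocol.

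Section 2.8.4 is more general: "Data will be analyzed using descriptive and analytic statistics". Its variables include TB contact, congregate settings, room size, ventilation and airflow, and also "use of public transportation (e.g. daladala buses); socioeconomic status, nutritional status, and underlying disease".

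Section 14 describes itself as giving the overall approach and defers detail to a separate SAP, which is not available here.

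**The concern.** The objective is to identify risk factors. A two-group test answers a narrower question: does this item differ between IGRA-positive and IGRA-negative adolescents? It cannot say whether the item still matters once the others are taken into account.

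Several listed items plausibly go together. Room size, ventilation, nutrition and use of public transport may all vary with socioeconomic status. If one of them drives infection, the others can differ between the groups merely because they accompany it. With 350 positives and 650 negatives, even a modest borrowed difference can reach significance.

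At stake is the interpretation of a secondary objective that is meant to be published in its own right. A reader of that paper could take a companion of the true factor for a risk factor.

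**Working it through.** The protocol states no power, precision or error rate for this objective, so there is no figure to reproduce. The group sizes are consistent: 650 + 350 = 1,000, or 35% positive.

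**Inputs from the protocol:** 650 IGRA-negative and 350 IGRA-positive subjects (Section 2.4); four unadjusted tests (Section 14.3(1)).

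**Assumed inputs, because the protocol gives none:**
- A true risk factor C is present in 50% of subjects, with odds ratio 2.
- An exposure X has no effect of its own, but its prevalence differs between subjects with and without C: 60% vs 30%, or 70% vs 30%.
- Each test is two-sided at 0.05. The protocol attaches 0.05 only to the log-rank test.

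**Step 1, risk by C.** Solve for the intercept *a* so that the average risk is 35%: 0.5·expit(a + ln 2) + 0.5·expit(a) = 0.35. This gives a = −0.984, a risk of 0.4279 with C and 0.2721 without.

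**Step 2, crude odds ratio for X.** The risk in each X group is the mix of the two C risks.

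| | X in 60% vs 30% | X in 70% vs 30% |
|---|---|---|
| Correlation of X with C (phi) | 0.30 | 0.40 |
| P(C given X); P(C given no X) | 0.667; 0.364 | 0.70; 0.30 |
| Risk with X | 0.667×0.4279 + 0.333×0.2721 = 0.3760 | 0.70×0.4279 + 0.30×0.2721 = 0.3811 |
| Risk without X | 0.364×0.4279 + 0.636×0.2721 = 0.3288 | 0.30×0.4279 + 0.70×0.2721 = 0.3189 |
| Crude OR (true value 1) | (0.3760/0.6240)/(0.3288/0.6712) = 1.23 | (0.3811/0.6189)/(0.3189/0.6811) = 1.32 |

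**Step 3, chance that the unadjusted test flags X.** Compare the prevalence of X in positives and negatives. The standard error is √[p(1−p)(1/650 + 1/350)], with p the overall prevalence of X.
- 60% vs 30%: 0.4834 vs 0.4320, difference 0.0513, standard error 0.0330. Φ(0.0513/0.0330 − 1.96) is about 0.34; simulation gives about 35%.
- 70% vs 30%: 0.5445 vs 0.4760, difference 0.0684, standard error 0.0331. Φ(0.0684/0.0331 − 1.96) is about 0.54; simulation gives 54–55%.

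**Step 4, after adjustment.** In simulated studies of 1,000, a logistic model containing X and C flags X in about 5% of studies in both scenarios.

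**Step 5, sensitivity.** Both exposures are at 50% prevalence; entries are the chance that the unadjusted test flags X.

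| OR of C | phi 0 | phi 0.2 | phi 0.4 | phi 0.6 |
|---|---|---|---|---|
| 1.5 | 5% | 9% | 23% | 45% |
| 2 | 5% | 18% | 54% | 87% |
| 3 | 5% | 36% | 90% | >99% |

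**Feasibility.** With 350 positives, a model with 15 parameters has 350/15, or about 23, events per parameter.

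**The case against.** The strongest reply is that an adjusted model is ordinary SAP content. Section 14 gives only the overall approach, 14.3(1) applies the tests where appropriate, and 2.8.4 leaves analytic statistics open. Nothing forbids a model. This stands as far as it goes: the four tests are the only methods named, not the only ones permitted. But the protocol is not silent. It names methods for this objective, and those methods alone cannot separate overlapping exposures.

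A reader might infer that the SAP will leave risk factors out, because Section 14 says it will "specify additional statistical methods to be used for analysis of safety, efficacy and pharmacokinetics". The text does not support that. The list includes pharmacokinetics, for which the schedule of events has no sampling, so it is not a reliable guide to what the SAP covers.

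A reader might also infer that the plan is bound to report false risk factors. The documents do not support that either. They report no correlation between exposures and set no significance rule for declaring a risk factor. With no correlation the chance is the nominal 5%. Confounding by age is limited by the 13–15 year range.

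Two further objections stand. Putting every factor into one model is not neutral: room size, ventilation or nutrition may lie on the path from socioeconomic status to infection, and adjusting for them can hide its effect. The simulated benefit assumes that C is a pure confounder. Nor does a multivariable model remove the multiplicity of testing many factors. Finally, crude effect sizes can be obtained from the planned descriptive statistics, so the gap is in adjusted estimates, not in effect sizes as such.

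**Conclusion.** The point holds as a low-cost improvement to a secondary, observational analysis. The only methods that 14.3(1) names for identifying risk factors are unadjusted, and they can flag an exposure with no effect of its own. In the two worked scenarios this happens in about 35% and 54% of studies, against about 5% after adjustment. Over the wider assumed range it runs from 5% to over 99%.

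These figures rest on assumed exposure correlations, an assumed true odds ratio and an assumed 0.05 threshold. They show that the effect can be large at this sample size, not that it will be. The randomised comparison, the efficacy endpoints, safety and the sample size are untouched.

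**What to change.** In Section 14.3(1), add a pre-specified multivariable logistic regression of baseline IGRA status on all screened subjects. Include age, sex and a set of covariates drawn from Section 2.8.4 and fixed in advance. When choosing the set, decide which factors may be mediators of socioeconomic status and how they will be treated. Report adjusted odds ratios with 95% confidence intervals beside the unadjusted comparisons. Keep the four tests as description and label their results unadjusted.

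Section 2.4 also promises that "Risk factor analysis will also be conducted on subjects enrolled in the immunization phase who develop new TB infection during the study". The model for that analysis can be left to the SAP.

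The cost is wording only: the analysis uses data already planned. The downside is that the covariate set must be chosen before the data are examined.

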## 8. SUBJECT SELECTION

### 8.1 Source of Subjects and Recruitment Methods

Following appropriate Human Studies review and approval, the Investigator may initiate and manage subject recruitment. This will include contact with the Ministries responsible for Education and Health in Tanzania and administrative leaders of secondary schools in Dar es Salaam. To reach an economically and socially diverse population, the study may be announced in newspapers, on the radio, at school functions and on relevant Internet websites.

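### The baseline risk-factor comparison names only tests for independent subjects, so p-values may be too small for exposures shared within a school or household

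*Protocol*

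**What the plan says.** Identifying risk factors for TB infection is a secondary objective (Protocol 2.2.2 and 6.2), and section 16.5 plans a separate publication on it. The baseline part is cross-sectional. Section 14.3, part 1: "All screened subjects will be included in this analysis which will compare subjects who test positive for IGRA at baseline and those who test negative". Section 2.4 gives the expected size: "estimated 650 IGRA-negative and 350 IGRA-positive subjects". The methods named in 14.3 are: "Pearson chi-square, Fisher's exact, t-test and Wilcoxon-Mann-Whitney tests will be used as appropriate". No allowance for school, household or community is mentioned.

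On recruitment, section 8.1 says it will include contact with the education and health ministries and with "administrative leaders of secondary schools in Dar es Salaam". It adds that "the study may be announced in newspapers, on the radio, at school functions and on relevant Internet websites". Schools are therefore a definite route but not the only one, and no cluster sampling scheme is described.

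On exposures, section 2.8.4 begins: "Variables will include household or community contact with TB, residence or exposure to congregate settings". It goes on to "room size; ventilation systems (windows); airflow patterns", public transport and socioeconomic status. The same list contains variables that belong mainly to the individual, such as nutritional status and underlying disease.

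**The concern.** The four named tests take their null variance from independent observations. Adolescents from the same school tend to share neighbourhood, transport and economic background, and those from the same household share rooms, ventilation and TB contacts. TB is transmissible, so IGRA status can be correlated within the same groups. If both the exposure and the outcome are correlated within clusters, about 1,000 screened adolescents carry less information on that association than 1,000 independent ones, and the test rejects a true null too often.

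At stake is the credibility of the risk factors reported from this analysis. The environmental exposures of most interest are the ones most likely to be affected. Adjusting for covariates does not remove the problem as long as the standard errors still assume independence.

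**Working it through.** The protocol gives no power, ICC or cluster size for this analysis, so there is no stated figure to reproduce. The check asks how far the true type I error of a nominal 5% test can drift.

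**From the documents:** N = 1,000 screened and 350 IGRA-positive, that is 35% (section 2.4); tests for independent subjects (14.3).

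**Assumed:** cluster size m; outcome ICC ρ_y; exposure ICC ρ_x; two-sided nominal 5%. Section 14.3 attaches p < 0.05 to the efficacy log-rank test only.

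**Formulas:**
- Design effect: DE = 1 + (m − 1) × ρ_y × ρ_x
- True type I error: 2 × [1 − Φ(1.96/√DE)]

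**Example.** With m = 50, ρ_y = 0.05 and ρ_x = 0.3, DE = 1 + 49 × 0.015 = 1.735. Then 1.96/√1.735 = 1.488, and the true error is 13.7%.

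The simulated column is the rejection rate of the Pearson chi-square test in clustered (beta-binomial) data with N = 1,000, 35% IGRA-positive, an assumed 30% exposed and 4,000 replicates. The Monte Carlo standard error near 5% is √(0.05 × 0.95/4000) = 0.3 percentage points.

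| Setting | m | ρ_y | ρ_x | DE | Formula | Simulated |
|---|---|---|---|---|---|---|
| Exposure not clustered | 50 | 0.05 | 0 | 1.00 | 5.0% | 5.0% |
| Household pairs, partly shared | 2 | 0.1 | 0.3 | 1.03 | 5.3% | 5.8% |
| Household pairs, fully shared | 2 | 0.1 | 1 | 1.10 | 6.2% | 6.2% |
| School, modest ICCs | 50 | 0.02 | 0.02 | 1.02 | 5.2% | 5.7% |
| School, modest ICCs | 50 | 0.02 | 0.1 | 1.098 | 6.1% | 6.5% |
| School, modest ICCs | 50 | 0.05 | 0.1 | 1.245 | 7.9% | 7.7% |
| School, strongly shared | 50 | 0.05 | 0.3 | 1.735 | 13.7% | 13.1% |
| School, fully shared | 50 | 0.05 | 1 | 3.45 | 29% | 30% |

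Formula and simulation agree to within about half a percentage point in every row but the last, where they differ by about one.

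The exposure ICC matters as much as the outcome ICC. The simpler design effect 1 + (m − 1) × ρ_y is the special case ρ_x = 1, in which every subject in a school has the same exposure. At m = 50 and ρ_y = 0.02 that case gives DE = 1.98 and 16%; at ρ_x = 0.1 it falls to 6.1%, and at ρ_x = 0.02 to 5.2%.

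**The case against.** The strongest reply is that section 14 describes only the overall approach and promises a detailed SAP, which is not shown. The tests are to be used as appropriate, and nothing rules out a clustered model later. That would answer a plain omission. Here, however, the protocol names its tests for a stated objective, and section 14 says the SAP will incorporate these sections. All the named tests rest on the same assumption, so the choice can fairly be questioned now.

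Three other points stand and limit the claim:
- **Recruitment.** A reader might infer that the sample is drawn by school. Section 8.1 does not say so; it also allows open announcements. Siblings are never mentioned, and the 13–15 age limit keeps sibling clusters small.
- **Scope.** A reader might infer that all p-values in this analysis are too small and that false risk factors will be reported. The documents do not support that. Inflation needs both IGRA status and the exposure to cluster, neither is quantified, and no variable in 2.8.4 is said to be measured at school level.
- **Incident infections.** A reader might extend the point to the risk-factor analysis of new infections in section 2.4. No tests are named there, so there is nothing stated to correct.

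**Conclusion.** The point holds in conditional form. The named tests are anti-conservative for exposures that cluster together with IGRA status, and p-values for individual-level exposures are little affected. Under the assumed values the true error of a nominal 5% test runs from no inflation (5%), through small (about 5–8%), to large (14–29%). The large values need an exposure strongly or fully shared within schools of 50 and an outcome ICC of 0.05. The documents do not supply the inputs to choose a point in this range, and the 5% level is itself assumed.

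This is an observational secondary objective. The randomised comparison of DAR-901 with placebo is not affected.

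**What to change.** - Record a school and a household identifier for every screened adolescent, including those who come through open announcements. The risk-factor interview at screening (Table 1) is a natural place. Without identifiers the problem cannot be repaired reliably afterwards.
- In section 14.3, part 1, base inference on logistic regression of baseline IGRA status that allows for clustering by school and household, with cluster-robust (GEE) standard errors or a random intercept. Keep the four named tests as descriptive.
- Provide for a small-sample correction if schools are few. With 50 per school, 1,000 screened means only 1,000/50 = 20 schools.

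The cost is a few lines of protocol or SAP text, two data fields and somewhat wider confidence intervals. If clustering proves negligible, the results will hardly change.
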